APPENDIX V: Patient Perception of Bladder Condition (PPBC)

Which of the following statements describes your bladder condition best at the moment's
Please mark "X" in one box only.
My bladder condition does not cause me any problems at all.
My bladder condition causes me some very minor problems.
My bladder condition causes me some minor problems.
My bladder condition causes me (some) moderate problems.
My bladder condition causes me severe problems.
My bladder condition causes me many severe problems.

APPENDIX VI: Parkinson's Impact Scale (PIMS) – **REDACTED** – **permission** required

APPENDIX VII: Epworth Sleepiness Scale (ESS) REDACTED License required http://epworthsleepinessscale.com/

APPENDIX VIII: Parkinson's Fatigue Scale (PFS)

REDACTED – can be accessed at www.parkinsons.org.uk/professionals/resources/parkinsons-disease-fatigue-scale

APPENDIX IX: Beck Depression Inventory-II (BDI-II)

REDACTED – Permission required. www.pearsonclinical.co.uk

APPENDIX X: Beck Anxiety Inventory (BAI)

REDACTED – Permission required. www.pearsonclinical.co.uk

APPENDIX XI: Constipation Questions

The following questions will be asked to establish the number of Rome II criteria each subject meets:

Over the last 2 weeks,

- 1. Did you have to strain at least 1 out of 4 times when having a bowel movement?
- 2. Did you have lumpy or hard stools at least 1 out of 4 times when having a bowel movement?
- 3. Did you have a sense of incomplete evacuation at least 1 out of 4 times when having a bowel movement?
- 4. Did you have a sensation of obstruction or blockage in your anal area at least 1 out of 4 time when having a bowel movement?
- 5. Did you have to use manual maneuvers to facilitate bowel movements at least 1 out of 4 times when having a bowel movement?
- 6. Did you have less than 3 bowel movements per week?

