3.9.3 Randomization (Visit 3; Day 0)

Randomization visit procedures will aim at collecting data that will be utilized as baseline measures for the statistical analysis for primary and secondary outcomes, and exploratory analyses.

- Concomitant medications
- Adverse events
- Study drug compliance
- Vital signs, weight, height, and orthostatics
- OABO
- 3-day VD assessment
- PPBC
- CQ
- UPDRS-6
- MoCA
- Map Search
- Hopkins Verbal Learning Test (HVLT)
- Trail Making Test (TMT) parts A and B
- Beck Anxiety Inventory (BAI)
- Beck Depression Inventory version II (BDI-II)
- Epworth Sleepiness Scale (ESS)
- Parkinson Fatigue Scale (PFS)
- Parkinson's Impact Scale (PIMS)
- Study drug dispense

At the conclusion of the randomization visit, subjects will be randomized in a double-blind fashion in a ratio of 2:1 to mirabegron 25 mg daily vs. placebo. Study drug will be administered in the form of 1 mirabegron 25 mg extended release matching placebo tablet daily (placebo arm) or 1 mirabegron 25 mg extended release tablet daily (active treatment arm). Thus all subjects will continue to receive 1 tablet daily. Sufficient study drug will be dispensed to last until Visit 6.

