3.10.3.4 Constipation Questions (CQ – Appendix XI)

Subjects will be asked a series of 6 questions to establish if they meet the Rome II criteria for constipation.⁴⁴ The Rome II committee defined functional constipation as occurrence of 2 or more of the symptoms listed in Appendix XI for at least 12 weeks, which need not be consecutive, in the preceding 12 months and in the absence of structural and biochemical explanation. The criteria exclude subjects presenting with loose stool episodes and irritable bowel syndrome. For the purpose of this study, the reference period will be the preceding 2 weeks to conform with the timeline of the study. The questions will be administered by the investigator or designee.

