6.1.11 Prior and concomitant medications

All concomitant medication that the subject is taking from the screening visit should be recorded on the concomitant medications log. In addition, any changes in concomitant medication or new medications added, including as a result of an inter-current illness must be recorded in the case report forms at each visit.

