7.4.3 Summary of exploratory data

The exploratory objectives are to assess effects of mirabegron on orthostatic changes in blood pressure, depressive and anxiety symptomatology, excessive salivation, constipation and PD motor symptom severity in PD patients with OAB symptoms and CI. The related hypotheses are that mirabegron will not impact these symptoms. The goal is to demonstrate equivalent symptoms prior to and following treatment with mirabegron as well as change compared to the placebo group. Tests of equivalence will be performed using the two one-sided tests approach on change from visit 3 to visit 7 in related variables within groups as well as between the two groups. Equivalence ranges will be determined for each measure based on available literature prior to data analysis.

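### The exploratory constipation equivalence test ignores laxatives started or increased on treatment, so constipation controlled before Visit 7 is wholly or partly hidden from it

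*Combined protocol and SAP*

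**What the plan says.** - **The score.** Appendix XI lists six yes/no questions: "The following questions will be asked to establish the number of Rome II criteria each subject meets". Five concern symptoms or stool frequency, for example "Did you have less than 3 bowel movements per week". The only aid to defecation asked about is manual: "Did you have to use manual maneuvers to facilitate bowel movements at least 1 out of 4 times when having a bowel movement". No item concerns a laxative, stool softener or enema.
- **The window.** Section 3.10.3.4: "For the purpose of this study, the reference period will be the preceding 2 weeks to conform with the timeline of the study".
- **The timing.** Table 1 and sections 3.9.3 and 3.9.7 place the questions at Visits 3 and 7 only. Visit 3 is the baseline: "Randomization visit procedures will aim at collecting data that will be utilized as baseline measures for the statistical analysis".
- **The analysis.** Section 7.4.3 applies two one-sided tests to the Visit 3 to Visit 7 change, within and between groups. "The related hypotheses are that mirabegron will not impact these symptoms". The equivalence range is to be set later.
- **Medication.** Section 6.1.11 has the CRF record "any changes in concomitant medication or new medications added". Section 6.1.12 does not name laxatives; it lets the Principal Investigator bar drugs that may alter outcome measures.
- **Adverse events.** Section 2.3 says that worsening of these symptoms is logged as an adverse event. Section 7.4.4 summarises adverse events overall and by group.

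**The concern.** In a superiority test, symptomatic treatment usually dilutes the claim. In an equivalence test it helps the claim, because successful treatment brings the Visit 7 score back towards its Visit 3 value. A subject who becomes constipated on mirabegron, starts a laxative and is well controlled for the last 2 weeks can contribute a change near zero to a test whose favourable result is no change.

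The within-mirabegron test is the most exposed, since it has no placebo arm in which laxative use could offset the effect. The synopsis rationale names constipation among the problems that mirabegron may not exacerbate, so an equivalence result would probably be cited even though the outcome is exploratory.

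**Working it through.** **1. Plan's own figure.** There is none to reproduce. Section 7.1 reports no sample size calculation, and 7.4.3 gives no constipation margin or SD. The only inputs are 30 subjects at 2:1, so 20 and 10, and the 0.05 level in 7.4.

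**2. Window.** Visit 7 is Day 84, and 84 − 14 = 70. Constipation that starts after Day 0 and is controlled by about Day 70 can leave no trace in the score. If control is partial, only part of the worsening is hidden.

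**3. Direction, by hand.** Assumptions, not in the documents: margin ±1 criterion, SD of change 1.0, pooled test.

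- SE = 1.0 × √(1/20 + 1/10) = 0.387.
- The 95th percentile of t on 28 df is 1.701, so the half-width is 1.701 × 0.387 ≈ 0.659.
- Equivalence needs an observed difference within ±(1 − 0.659) = ±0.341.
- True difference 1.0, nothing hidden: Φ((0.341 − 1.0)/0.387) = Φ(−1.70) ≈ 4% (simulation: 5%).
- Half the mean worsening hidden, true difference 0.5: Φ(−0.41) − Φ(−2.17) ≈ 33% (simulation: 33%).

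With half hidden, the same simulation gives 51% at SD 0.75, 18% at SD 1.25 and 6% at SD 1.5. With nothing hidden it gives 5%, 4% and 2%.

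**4. Worsening concentrated in some subjects.** Assumptions: 25–50% of the mirabegron arm gain 4 to 2 criteria (arm mean +1), margin ±1, Welch test between groups and a one-sample test within mirabegron. The SD here is residual scatter. The change in the active arm varies more: if 25% gain 4, that alone adds an SD of 4 × √(0.25 × 0.75) = 1.73. Ranges cover both shares and two codings of a treated subject (usual scatter around zero, or exactly zero).

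| Worsened subjects hidden | Between, SD 1.0 | Between, SD 1.5 | Within mirabegron, SD 1.0 | Within mirabegron, SD 1.5 |
|---|---|---|---|---|
| 0% | 5% | 1% | 5–7% | 5–6% |
| 25% | 11–13% | 2–3% | 19–21% | 14–17% |
| 50% | 22–29% | 3–7% | 40–55% | 29–41% |
| 75% | 39–51% | 6–12% | 72–90% | 51–75% |

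**5. At rates in the documents.** Section 6.1.2 gives constipation as 1.6% on mirabegron 50 mg against 1.4% on placebo, and 2.8% against 2.7% on active control in Study 4. Among 20 subjects that is 20 × 0.016 = 0.32 to 20 × 0.028 = 0.56 expected cases. Suppose each case gains 3 criteria (assumed). The between-group chance of equivalence at SD 1.0 is then 54–57% with nothing hidden and 59–60% with every case hidden. At SD 1.5 it is 8–9% and about 10%. The mean worsening is only 0.016 × 3 = 0.05 to 0.028 × 3 = 0.08 criteria, far inside a margin of 1, so equivalence would not be a false conclusion here.

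**The case against.** **Treated constipation is not lost to the trial.** A reader might infer that the plan removes this harm from the evidence. The documents do not support that. Section 2.3 requires worsening to be logged as an adverse event, Table 1 collects events from Visit 2 to Visit 8, and 7.4.4 reports them by group. This stands. What remains is that the dedicated measure could read as equivalent while the adverse event table shows treated cases.

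**The large percentages need heavy worsening.** A reader might take 22–29% or 40–55% as the expected error. They hold only if a quarter to a half of the mirabegron arm worsens by 4 to 2 criteria, far above the rates in 6.1.2. This also stands, with one limit: those rates come from general overactive-bladder trials, and the documents give none for Parkinson disease.

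**The direction is not wholly one-sided.** Placebo laxative use partly offsets the between-group bias, though not the within-mirabegron test. A subject already constipated at Visit 3 who then starts a laxative may improve beyond baseline, which moves the change away from zero.

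**Symptoms at end of treatment regardless of laxatives is a legitimate outcome.** Agreed, and it should stay. The weakness is to read it alone as no impact on constipation. The Principal Investigator's power to bar drugs that alter outcomes is discretionary and does not settle how the analysis treats them.

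**Loose stools.** One could also fault the form for having no loose-stool item, because 3.10.3.4 says "The criteria exclude subjects presenting with loose stool episodes and irritable bowel syndrome". That sentence describes the Rome II definition of functional constipation, whereas Appendix XI counts criteria met. No role for such an item in the analysis is evident, so that criticism is not made.

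**Conclusion.** The gap is real but minor. The score sees only the 2 weeks before each of two visits, no item covers laxatives, and 7.4.3 does not use the laxative data that 6.1.11 already collects. Treated constipation on mirabegron is therefore wholly or partly hidden from this one test, in the direction of no impact and most clearly within the mirabegron group.

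The size cannot be fixed from the documents. It depends on the margin, the SD, the share of subjects who worsen and how fully laxatives control them, none of which is given. If Parkinson rates resemble those in 6.1.2, the between-group result moves by about 6 percentage points at most. If constipation were much more common in this population, the effect could be large. The outcome is exploratory, in a 30-subject pilot, and the primary cognitive analysis is unaffected.

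**What to change.** 1. Keep the planned two one-sided tests on the symptom count.
2. Add one yes/no item to Appendix XI at Visits 3 and 7: any laxative, stool softener or enema in the last 2 weeks.
3. Prespecify a companion analysis in 7.4.3. A subject counts as worsened if at least one more criterion is met at Visit 7 than at Visit 3, or if the medication log shows a laxative started or increased after Visit 3. Report the proportions by arm and their difference with a confidence interval, beside the constipation adverse event counts.
4. State that equivalence on constipation will not be claimed from the symptom count alone if the companion analysis disagrees, and define disagreement when the margin is set.
5. State that a non-significant difference in proportions is not evidence of no impact. For illustration, with 4 of 20 and 2 of 10 worsened the difference is 0, its SE is √(0.16/20 + 0.16/10) = 0.155, and the approximate 95% interval is ±30 percentage points. For that reason the companion analysis should not replace the planned test.

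**Cost.** One extra question on a staff-administered form and one derivation from an existing log. Even without the new item, the companion analysis can be built from the log. The downside is that a laxative started for another reason counts as worsening; the symptom-count row shows how much that matters. Who may take laxatives does not change.

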APPENDIX XII: Unified Parkinson's Disease Rating Scale (UPDRS)

Unified Parkinson's Disease Rating Scale

i. Mentation, Behavior and Mood

1. Intellectual Impairment

- 0 = None
- 1 = Mild. Consistent forgetfulness with partial recollection of events and no other difficulties.
- 2 = Moderate memory loss, with disorientation and moderate difficulty handling complex problems. Mild but definite impairment of function at home with need of occasional prompting.
- 3 = Severe memory loss with disorientation for time and often to place. Severe impairment in handling problems.
- 4 = Severe memory loss with orientation preserved to person only. Unable to make judgements or solve problems. Requires much help with personal care. Cannot be left alone at all.

2. Thought Disorder [Due to dementia or drug intoxication.]

- 0 = None.
- 1 = Vivid dreaming.
- 2 = "Benign" hallucinations with insight retained.
- 3 = Occasional to frequent hallucinations or delusions; without insight; could interfere with daily activities.
- 4 = Persistent hallucinations, delusions, or florrid psychosis. Not able to care for self.

3. Depression

- 0 = Not present.
- 1 = Periods of sadness or guilt greater than normal, never sustained for days or weeks.
- 2 = Sustained depression (1 week or more).
- 3 = Sustained depression with vegetative symptoms (insomnia, anorexia, weight loss, loss of interest).
- 4 = Sustained depression with vegetative symptoms and suicidal thoughts or intent.

4. Motivation/initiative

- 0 = Normal.
- 1 = Less assertive than usual; more passive.
- 2 = Loss of initiative or disinterest in elective (non-routine) activities.
- $\mathbf{3} = \mathbf{Loss}$ of initiative or disinterest in day to day (routine) activities.
- 4 = Withdrawn, complete loss of motivation.

il. Activities of Daily Living [For both "on" and "off."]

5. Speech

- 0 = Normal.
- 1 = Mildly affected. No difficulty being understood.
- 2 = Moderately affected. Sometimes asked to repeat statements.
- 3 = Severely affected. Frequently asked to repeat statements. 4 = Unintelligible most of the time.

6. Salivation

- 0 = Normai.
- 1 = Slight but definite excess of saliva in mouth; may have nighttime drooling.
- 2 = Moderately excessive saliva; may have minimal drooling.
- 3 = Marked excess of saliva with some drooling.
- 4 = Marked drooling, requires constant tissue or handkerchief.

7. Swallowing

- 0 = Normal.
- 1 = Rare choking.
- 2 = Occasional choking.
- 3 = Requires soft food.
- 4 = Requires NG tube or gastrostomy feeding.

8. Handwriting

- 0 = Normal.
- 1 = Slightly slow or small.
- 2 = Moderately slow or small; all words are legible.
- 3 = Severely affected; not all words are legible.
- 4 = The majority of words are not legible.

9. Cutting food and handling utensils

- 0 = Normal.
- 1 = Somewhat slow and clumsy, but no help needed.
- 2 = Can cut most foods, although clumsy and slow; some help needed.
- 3 = Food must be cut by someone, but can still feed slowly.
- 4 = Needs to be fed.

10. Dressing

- 0 = Normal.
- 1 = Somewhat slow, but no help needed.
- 2 = Occasional assistance with buttoning, getting arms in sleeves.
- 3 = Considerable help required, but can do some things alone.
- 4 = Helpless.

11. Hygiene

- 0 = Normal.
- 1 = Somewhat slow, but no help needed.
- 2 = Needs help to shower or bathe; or very slow in hygienic care.
- 3 = Requires assistance for washing, brushing teeth, combing hair, going to bathroom.
- 4 = Foley catheter or other mechanical aids.

12. Turning in bed and adjusting bed clothes

- 0 ≠ Normai
- 1 = Somewhat slow and clumsy, but no help needed.
- 2 = Can turn alone or adjust sheets, but with great difficulty.
- 3 = Can initiate, but not turn or adjust sheets alone.
- 4 = Helpless.

13. Falling [Unrelated to freezing.]

- 0 = None.
- 1 = Rare falling.
- 2 = Occasionally falls, less than once per day.
- 3 = Falls an average of once daily.
- 4 = Falls more than once daily.

14. Freezing when walking

- 0 = None.
- 1 = Rare freezing when walking; may have start-hesitation.
- 2 = Occasional freezing when walking.
- 3 = Frequent freezing. Occasionally falls from freezing.
- 4 = Frequent falls from freezing.

15. Walking

- 0 = Normal.
- 1 = Mild difficulty. May not swing arms or may tend to drag
- 2 = Moderate difficulty, but requires little or no assistance.
- 3 = Severe disturbance of walking, requiring assistance.
- 4 = Cannot walk at all, even with assistance.

- 16. Tremor [Symptomatic complaint of tremor in any part of body.]
 - 0 = Absent.
 - 1 = Slight and infrequently present.
 - 2 = Moderate; bothersome to patient.
 - 3 = Severe; interferes with many activities.
 - 4 = Marked; interferes with most activities.

17. Sensory complaints related to parkinsonism

- 0 = None.
- 1 = Occasionally has numbness, tingling, or mild aching.
- 2 = Frequently has numbness, tingling, or aching; not distressing.
- 3 = Frequent painful sensations.
- 4 = Excruciating pain.

III. Motor Examination

18. Speech

- 0 = Normal.
- 1 = Slight loss of expression, diction and/or volume.
- 2 = Monotone, slurred but understandable; moderately impaired.
- 3 = Marked impairment, difficult to understand.
- 4 = Unintelligible.

19. Facial Expression

- 0 = Normal.
- 1 = Minimal hypomimia, could be normal "Poker Face".
- 2 = Slight but definitely abnormal diminution of facial expression
- 3 = Moderate hypomimia; lips parted some of the time.
- 4 = Masked or fixed facies with severe or complete loss of facial expression; lips parted 1/4 inch or more.

20. Tremor at rest

- 0 = Absent.
- 1 = Slight and infrequently present.
- 2 = Mild in amplitude and persistent. Or moderate in amplitude, but only intermittently present.
- 3 = Moderate in amplitude and present most of the time.
- 4 = Marked in amplitude and present most of the time.

21. Action or Postural Tremor of hands

- 0 = Absent.
- 1 = Slight; present with action.
- 2 = Moderate in amplitude, present with action.
- 3 = Moderate in amplitude with posture holding as well as action.
- 4 = Marked in amplitude; interferes with feeding.
- Rigidity [Judged on passive movement of major joints with patient relaxed in sitting position; ignore cogwheeling.]
 - 0 = Absent.
 - 1 = Slight or detectable only when activated by mirror or other movements.
 - 2 = Mild to moderate.
 - 3 = Marked, but full range of motion easily achieved.
 - 4 = Severe, range of motion achieved with difficulty.
- 23. Finger Taps (Patient taps thumb with index finger in rapid succession with widest amplitude possible, each hand separately.)
 0 = Normal.
 - 1 = Mild slowing and/or reduction in amplitude.
 - 2 = Moderately impaired. Definite and early fatiguing. May have occasional arrests in movement.
 - 3 = Severely impaired. Frequent hesitation in initiating movements or arrests in ongoing movement.

- 4 = Can barely perform the task.
- 24. Hand Movements [Patient opens and closes hands in rapid succession with widest amplitude possible, each hand separately.]
 - 0 = Normal
 - 1 = Mild slowing and/or reduction in amplitude.
 - 2 = Moderately impaired. Definite and early fatiguing. May have occasional arrests in movement.
 - 3 = Severely impaired. Frequent hesitation in initiating movements or arrests in ongoing movement.
 - 4 = Can barely perform the task.
- Rapid Alternating Movements of Hands [Pronation-supination movements of hands, vertically or horizontally, with as large an amplitude as possible, each hand separately.]
 - 0 = Normal
 - 1 = Mild slowing and/or reduction in amplitude.
 - 2 = Moderately impaired. Definite and early fatiguing. May have occasional arrests in movement.
 - 3 = Severely impaired. Frequent hesitation in initiating movements or arrests in ongoing movement.
 - 4 = Can barely perform the task.
- 26. Leg Agility [Patient taps heel on ground in rapid succession, picking up entire leg. Amplitude should be about 3 inches.]
 - 0 = Normal.
 - 1 = Mild slowing and/or reduction in amplitude.
 - 2 = Moderately impaired. Definite and early fatiguing. May have occasional arrests in movement.
 - 3 = Severely impaired. Frequent hesitation in initiating movements or arrests inongoing movement.
 - 4 = Can barely perform the task.
- 27 Arising from chair [Patient attempts to arise from a straight-back wood or metal chair with arms folded across chest.]
 - 0 = Normal.
 - 1 = Slow; or may need more than one attempt.
 - 2 = Pushes self up from arms of seat.
 - 3 = Tends to fall back and may have to try more than one time, but can get up without help.
 - 4 = Unable to arise without help.

28. Posture

- 0 = Normal erect.
- 1 = Not quite erect, slightly stooped posture; could be normal for older person.
- 2 = Moderately stooped posture, definitely abnormal; can be slightly leaning to one side.
- 3 = Severely stooped posture with kyphosis; can be moderately leaning to one side.
- 4 = Marked flexion with extreme abnormality of posture.

29. Galt

- 0 = Normal.
- 1 = Walks slowly, may shuffle with short steps, but no festination (hastening steps) or propulsion.
- 2 = Walks with difficulty, but requires little or no assistance; may have some festination, short steps, or propulsion.
- 3 = Severe disturbance of gait, requiring assistance.
- 4 = Cannot walk at all, even with assistance.
- 30. Postural Stability [Response to sudden, strong posterior displacement produced by pull on shoulders while patient erect with eyes open and feet slightly apart. Patient is prepared, and can have had some practice runs.]
 - 0 = Normal.
 - 1 = Retropulsion, but recovers unaided.

- 2 = Absence of postural response; would fall if not caught by examiner.
- 3 = Very unstable, tends to lose balance spontaneously.
- 4 = Unable to stand without assistance.
- 31. Body Bradykinesia and Hypokinesia [Combining slowness, hesitancy, decreased armswing, small amplitude, and poverty of movement in general.]
 - 0 = None.
 - 1 = Minimal slowness, giving movement a deliberate character; could be normal for some persons. Possibly reduced amplitude.
 - 2 = Mild degree of slowness and poverty of movement which is definitely abnormal. Alternatively, some reduced amplitude.
 - 3 = Moderate slowness, poverty or small amplitude of movement.
 - 4 = Marked slowness, poverty or small amplitude of movement.

IV. Complications of Therapy [In the past week.]

A. DYSKINESIAS

- 32. Duration: What proportion of the waking day are dyskineslas present? [Historical Information.]
 - 0 = None
 - 1 = 1-25% of day.
 - 2 = 26-50% of day.
 - 3 = 51 75% of day.
 - 4 = 76-100% of day.
- 33. Disability: How disabling are the dyskinesias? [Historical information; may be modified by office examination.]
 - 0 = Not disabling.
 - 1 = Mildly disabling
 - 2 = Moderately disabling.
 - 3 = Severely disabling.
 - 4 = Completely disabled.
- 34. Painful Dyskinesias: How painful are the dyskinesias?
 - 0 = No painful dyskinesias.
 - 1 = Slight.
 - 2 = Moderate.
 - 3 = Severe.
 - 4 = Marked.
- 35. Presence of Early Morning Dystonia [Historical Information.]
 - 0 = No
 - 1 = Yes
- **B. CLINICAL FLUCTUATIONS**
- 36. Are any "off" periods predictable as to timing after a dose of medication?
 - $0 = N_0$
 - 1 = Yes
- 37. Are any "off" periods unpredictable as to timing after a dose of medication?
 - 0 = No
 - 1 = Yes
- 38. Do any of the "off" periods come on suddenly, e.g., over a few seconds?
 - 0 = No
 - 1 = Yes
- 39. What proportion of the waking day is the patient "off" on average?

- 0 = None
- 1 = 1-25% of day.
- 2 = 26-50% of day.
- 3 = 51 75% of day.
- 4 = 76-100% of day.

C. OTHER COMPLICATIONS

- 40. Does the patient have anorexia, nausea, or vomiting?
 - 0 = No
 - 1 = Yes
- 41. Does the patient have any sleep disturbances, e.g., insomnia or hypersomnolence?
 - 0 = No
 - 1 = Yes
- 42. Does the patient have symptomatic orthostasis? [Record the patient's blood pressure, height and weight on the scoring form.]
 - 0 = No
 - 1 = Yes

Modified	Hoehn and Yahr Staging
Stage 0	No signs of disease.
Stage 1	Unilateral disease.
Stage 1.5	Unilateral plus axial involvement.
Stage 2	Bilateral disease, without impairment of balance.
Stage 2.5	Mild bilateral disease, with recovery on pull test.
Stage 3	Mild to moderate bilateral disease; some postural instability; physically independent.
Stage 4	Severe disability; still able to walk or stand unassisted.
Stage 5	Wheelchair bound or bedridden unless aided.

VI. Schwab and England Activities of Daily Living Scale [It is O.K. to select a number in between the definitions.]

100% Completely independent. Able to do all chores without slowness, difficulty or impairment. Essentially normal. Unaware

- of any difficulty.

 90% Completely independent. Able to do all chores with some
- degree of slowness, difficulty and impairment, Might take twice as long. Beginning to be aware of difficulty.
- 80% Completely independent in most chores. Takes twice as long. Conscious of difficulty and slowness.

 70% Not completely independent. More difficulty with some
- chores. Three to four times as long in some. Must spend a large part of the day with chores.
- 60% Some dependency. Can do most chores, but exceedingly slowly and with much effort. Errors; some impossible.
- 50% More dependent. Help with half of chores, slower, etc. Difficulty with everything.
- 40% Very dependent. Can assist with all chores, but few alone.30% With effort, now and then does a few chores alone or be-
- gins alone. Much help needed.

 20% Nothing alone. Can be a slight help with some chores. Severe invalid.
- 10% Totally dependent, helpless. Complete invalid.
- 0% Vegetative functions such as swallowing, bladder and bowel functions are not functioning. Bed-ridden.
